3.2 Exclusion Criteria

- 3.2.1 Medical contraindication to receipt of radiotherapy.
- 3.2.2 Severe active co-morbid systemic illnesses or other severe concurrent disease which, in the judgment of the investigator, would make the patient inappropriate for entry into this study or interfere significantly with the proper assessment of safety and toxicity of the prescribed regimens.
- 3.2.3 Uncontrolled intercurrent illness including, but not limited to, ongoing or active infection, symptomatic congestive heart failure, unstable angina pectoris, cardiac arrhythmia, or psychiatric illness/social situations that would limit compliance with study requirements or providing informed consent.
- 3.2.4 Active systemic lupus or scleroderma.
- 3.2.5 Pregnancy.
- 3.2.6 Women of childbearing potential who are unwilling to employ adequate contraception.
- 3.2.7 Prior receipt of ipsilateral breast or chest wall radiation.
- 3.2.8 Recurrent breast cancer.
- 3.2.9 Indications for comprehensive regional nodal irradiation.

4.0 Test Schedule

¹ Highly suggested but not mandatory.

² Digital photographs can be done at any time before or after treatment at the discretion of the physician.

³ Last day of treatment +/- 2 days, per discretion of the treating physician.

⁴ Outside pathology must be reviewed at treating institution to confirm eligibility.

⁵ For women of childbearing potential only, blood pregnancy test to be completed prior to start of radiation.

⁶ Failure defined as recurrent disease.

⁷ For tissue: total of 4 samples will be collected (2 at pre-RT and 2 at surgery), see section 17.1 for details. For blood: total of 12 samples will be collected (6 at pre-RT and 6 at surgery), see section 14.1 for details.

5.0 Stratification Factors

5.1 None.

6.0 Registration

6.1 Registration Procedures

- 6.1.1 Patient will be registered to the study when they have consented, met eligibility criteria, and have been logged into the Research Participant Tracking (Ptrax) system.
- 6.1.2 Baseline tests/procedures (see section 4.0) will be completed within the guidelines specified on the test schedule.
- 6.1.3 All patients meeting eligibility criteria who have signed a consent form and who have completed treatment will be evaluable for the primary analysis. All patients completing treatment as per the study pre-op RT followed by breast conserving surgery will be used to determine the protocol accrual.
- 6.1.4 Patients consented and enrolled will be monitored in the registry, if patients signed our registry consent (IRB 16000492). All patient meeting accrual as defined in 6.1.3 will be analyzed per study.

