13.0 Treatment/Follow-up Decision at Evaluation of Patient

Follow-up data will be collected and entered after the observation phase outlined in section 4.0. If the patient is still alive after 5 years have elapsed from the on-study date, no further follow-up is required by this protocol.

- 13.1 Patients who have a recurrence while receiving therapy or during observation will go to the event-monitoring phase and be followed
- 13.2 Patients who discontinue treatment or observation for reasons other than recurrence will go to the event-monitoring phase and be followed
- 13.3 Patients who will not receive any radiation treatment or who will receive radiation treatment elsewhere will move to event monitoring phase.
- 13.4 A patient is deemed *ineligible* if after registration, it is determined that at the time of registration, the patient did not satisfy each and every eligibility criteria for study entry. The patient may continue treatment off-protocol at the discretion of the physician as long as there are no safety concerns, and the patient was properly registered. The patient will go directly to the event-monitoring phase of the study (or off study, if applicable).

If the patient received treatment, all data up until the point of confirmation of ineligibility must be submitted. Event monitoring will be required per Section 18.0 of the protocol.

If the patient never received treatment, on-study material and the End of Active Treatment/Cancel Notification Form must be submitted. No further data submission is necessary.

- 13.5 A patient is deemed a *cancel* if he/she is removed from the study for any reason before any study treatment is given. On-study material and the End of Active Treatment/Cancel Notification Form must be submitted. No further data submission is necessary.

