16.2 Primary and Secondary Endpoints

16.21 Primary Endpoint: The pathologic complete response (pCR) rate observed at time of definitive surgery in breast cancer patients receiving preoperative ionizing radiation. A residual tumor cancer burden 0-1 would be considered a pCR.³¹ All patients meeting eligibility criteria who have signed a consent form and who have begun treatment will be evaluable for the endpoint.

16.22 Secondary Endpoints:

16.221 Acute and late adverse events including grade ≥ 2 pneumonitis.

16.223 Locoregional control, invasive disease-free, distant recurrence, disease-free survival, cause-specific survival, overall survival.

The following definitions are used for the secondary endpoints of interest:

- *Pathologic complete response*: We defined a pathological complete response (pCR) as a residual tumor burden of 0-1 in the surgical specimen.³¹
- *Acute adverse events* (up to 180 days post-RT): any adverse event, regardless of attribution, that occurs in the first month post-RT.
- *Late adverse events* (up to 5 years post XRT): any adverse event that occurred after the first month post-RT and up to 5 years post-RT.
- *Ipsilateral breast tumor recurrence (IBTR)*: this is defined as local recurrence from trial registration as a first event at 5 years. IBTR is defined as both invasive and non-invasive breast cancer involving the same breast parenchyma as the original tumor.
- *Regional recurrence*: invasive breast cancer in the axilla, regional lymph nodes, chest wall, and skin of the ipsilateral breast at 5 years.
- *Distant recurrence*: metastatic cancer that has either been biopsy confirmed or clinically diagnosed as recurrent invasive breast cancer at 5 years.
- *Invasive disease-free survival*: this is defined as the time from study registration until the occurrence of one of the events in a composite endpoint. This endpoint includes invasive IBTR, regional invasive breast cancer recurrence, distant breast cancer recurrence, death due to any cause,
- *Disease-free survival*: this is defined as the time from study registration until the occurrence of one of the events in a composite endpoint. This endpoint includes any IBTR, regional invasive breast cancer recurrence, distant breast cancer recurrence, death due to any cause,

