16.52 Secondary Analyses

16.521 *Acute adverse events (up to 180 days post-RT):* All patients who were registered to the study and started treatment will be included in the acute adverse event analysis. An acute adverse event is an AE, regardless of attribution, that occurs up to 180 days post-RT. The maximum grade for each type of acute AE will be recorded for each patient. Data will be summarized as frequencies and relative frequencies. Additionally, the relationship of the adverse event(s) to the study treatment will be taken into consideration.

16.522 *Late adverse events:* All patients who were registered to the study and started treatment will be included in the late adverse event analysis. A late adverse event is an AE, regardless of attribution, that after one month post-RT and up to 5 years post-RT. The maximum grade for each type of late AE will be recorded for each patient. Data will be

summarized as frequencies and relative frequencies by treatment arm. Additionally, the relationship of the adverse event(s) to the study treatment will be taken into consideration.

- 16.523 *Locoregional control:* The cumulative incidence of locoregional recurrence will be estimated using a competing risks method (Gooley et al.). The competing risks will be distant breast cancer recurrence and death.
- 16.524 *Invasive disease-free survival:* i-DFS is defined as the time from registration until the time of disease recurrence or death due to any cause. The i-DFS will be estimated with a Kaplan-Meier estimator and curve. Estimates will be given for specific time points along with 95% CIs.
- 16.525 *Disease-free survival:* DFS is defined as the time from registration until the time of disease recurrence or death due to any cause. The DFS will be estimated with a Kaplan-Meier estimator and curve. Estimates will be given for specific time points along with 95% CIs.
- 16.526 *Cause specific survival:* The CSS will be estimated with a Kaplan-Meier estimator and curve. Estimates will be given for specific time points along with 95% CIs.
- 16.527 *Overall survival:* The OS will be estimated with a Kaplan-Meier estimator and curve. Estimates will be given for specific time points along with 95% CIs.

16.53 Exploratory Analyses:

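### Section 6.1.4 makes completers of RT and breast-conserving surgery the set analysed per study, in conflict with 16.52, 13.2 and 16.6; the time-to-event population and late adverse-event collection are left open

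*Combined protocol and SAP*

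**What the plan says.** Section 6.1.3 fixes what counts as accrual: "All patients completing treatment as per the study pre-op RT followed by breast conserving surgery will be used to determine the protocol accrual". Section 6.1.4 then places two groups side by side. Of the first it says: "Patients consented and enrolled will be monitored in the registry, if patients signed our registry consent". Of the second: "All patient meeting accrual as defined in 6.1.3 will be analyzed per study". Registry consent is not an eligibility criterion; 3.1.6 asks only for study-specific consent.

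Other sections say something different, or nothing:

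- **16.521:** "All patients who were registered to the study and started treatment will be included in the acute adverse event analysis". Section 16.522 uses the same set for late events, up to 5 years after RT.
- **16.523 to 16.527** give estimators for locoregional control, invasive disease-free, disease-free, cause-specific and overall survival, but no analysis population. The definitions under 16.22 time the four survival endpoints from registration.
- **13.2:** "Patients who discontinue treatment or observation for reasons other than recurrence will go to the event-monitoring phase and be followed". Section 16.6 likewise promises 5 years of follow-up within the study. Neither mentions registry consent.
- **18.1** marks the solicited and other adverse-event forms at end of treatment and in the observation phase. In event monitoring it marks only the Patient Status Form.

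**The concern.** Patients outside the 6.1.3 accrual definition are those who stop RT early, progress or die before surgery, decline surgery, or have a mastectomy. The last is a realistic route, because 3.1.8 requires only planned breast surgery and 7.11.1 leaves the operation to the surgeon. Most of these routes depend on what happens after RT starts, so leaving such patients out could be informative.

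Objectives 2.21 and 2.22 are to describe toxicity and 5-year outcome after preoperative radiation. If the time-to-event set is taken from 6.1.4, the estimates describe women who got through to breast-conserving surgery, not women who were treated. If adverse events are not recorded once a patient enters event monitoring, the all-treated late-event analysis in 16.522 has a denominator that includes her and a numerator that cannot.

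**Working it through.** **Step 1: the sets side by side.**

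| Purpose | Set | Source |
|---|---|---|
| Accrual count | RT completed, then breast-conserving surgery | 6.1.3 |
| Analysed per study | Same as the accrual count | 6.1.4 |
| Acute and late adverse events | Registered and started treatment | 16.521, 16.522 |
| Suspension rule | Treated patients | 16.62 |
| Time-to-event endpoints | Not stated | 16.523 to 16.527 |

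For adverse events, a specific rule in section 16 competes with 6.1.4. For the time-to-event endpoints nothing competes, and 6.1.4 is the nearest text on who is analysed.

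**Step 2: effect on the time-to-event endpoints.** The survival clocks start at registration. Membership of the 6.1.3 set is known only at surgery, which 7.11.2 allows 4 to 16 weeks after RT. Every member is therefore alive from registration to surgery by construction, and anyone who dies, withdraws or becomes inoperable in that interval is removed. The post-RT part alone is 4/260 = 1.5% to 16/260 = 6.2% of a 5-year (260-week) horizon. That fixed interval is short; the selection of patients matters more.

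**Step 3: how many patients.** Section 16.42 gives 22 evaluable + 3 allowance = 25. The allowance also covers ineligibility and cancellation, and 13.5 defines a cancel as removal before any study treatment. The number of treated non-completers is not in the documents; I assume 0 to 3. One patient in 25 moves a rate by 1/25 = 4.0 percentage points.

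**Step 4: direction.** Assumed counts: 2 events among 22 completers, 3 treated non-completers, y of them with an event. The completer rate is 2/22 = 9.1%; the all-treated rate is (2 + y)/25.

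| y | All-treated rate | Difference from 9.1% |
|---|---|---|
| 0 | 2/25 = 8.0% | −1.1 points |
| 1 | 3/25 = 12.0% | +2.9 points |
| 2 | 4/25 = 16.0% | +6.9 points |
| 3 | 5/25 = 20.0% | +10.9 points |

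With no treated non-completers the difference is zero. The sign depends on y, which is unknown.

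**Step 5: late adverse-event data.** A patient who discontinues goes to event monitoring (13.2), and so does one who recurs (13.1). Section 16.522 keeps both in the late analysis for 5 years, but 18.1 marks no adverse-event form for that phase. Following 13.2 alone would not supply the data. A patient who completes RT and then has a mastectomy has not discontinued; on a plain reading she stays in observation with her forms, and is affected only by the analysis-set wording.

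**Step 6: the pCR design.** The probability of 3 or more successes in 22 is 0.0948 at a true rate of 0.05 and 0.8455 at 0.20, matching the printed 0.09 and 0.85. Nothing here changes those figures.

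**The case against.** The strongest reply is that 6.1.4 excludes nobody. It does not contain the word only, names neither adverse events nor survival, sits among registration procedures, and follows a sentence about evaluability for the primary analysis. The statistician and study chair decide when to analyse (16.5) and have explicit adverse-event sets in 16.521 and 16.522. The suspension rule counts treated patients whatever 6.1.4 says, and 10.5 requires grade 4 and 5 events to be submitted regardless of attribution. Endpoints timed from registration also sit poorly with a completer set.

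Much of this stands. A reader might infer that 6.1.4 restricts the toxicity analysis to completers. The text does not go that far, and section 16 is more specific. A reader might also infer that study follow-up depends on registry consent. The sentence concerns monitoring inside a separate registry, while 13.2 and 16.6 provide study follow-up unconditionally.

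The reply does not cover the time-to-event analyses, for which section 16 names no population. Nor does it cover the forms in 18.1: grade 4 and 5 reporting does not capture grade 2 pneumonitis, grade 3 dermatitis or late fibrosis.

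**Conclusion.** The inconsistency is real and should be reconciled. Section 6.1.4 points to completers, 16.521 and 16.522 to all who started treatment, and 6.1.4 mentions only registry monitoring where 13.2 and 16.6 require study follow-up. The practical exposure is limited to the unstated population for 16.523 to 16.527 and to late adverse-event collection after a move to event monitoring.

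It is tempting to say that toxicity will be understated by 3 to 7 percentage points. The documents do not support that. The figure needs all 3 allowance patients to have been treated and 1 or 2 of them to have had an event; with none the completer rate is the higher one, and with no treated non-completers there is no difference. What can be said is that 0 to 3 patients may be affected by the analysis-set wording, at about 4 points each in 25, with unknown direction. Patients who recur add to those affected by the form schedule; the documents give no figure for them.

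**What to change.** Four wording changes:

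1. **6.1.4:** state that the 6.1.3 accrual definition is used only to count accrual.
2. **16.52:** state that every registered patient who starts RT is included in the adverse-event analyses and in the time-to-event analyses 16.523 to 16.527.
3. **6.1.4 and 13:** state that these patients are followed on the study consent whether or not they sign the registry consent.
4. **18.1:** mark the solicited and other adverse-event forms for treated patients in event monitoring. Without this, the other three changes do not secure the late data that 16.522 needs.

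The cost is a short amendment and slightly more data collection: up to about 3 treated non-completers, whom 13.2 already requires to be followed, plus any patient who moves to event monitoring after recurrence. Reported estimates may be less favourable. The amendment leaves open whether the pCR denominator is patients who completed treatment (6.1.3) or began it (16.21, 16.51), which is a separate matter.

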7.0 Protocol Treatment

Doses throughout will be prescribed in Gy or Gy(RBE). Radiation therapy must begin within 180 days of the last biopsy date. Concurrent cytotoxic chemotherapy with radiotherapy is not allowed.

7.1 Radiation Therapy**7.2 Dose Specifications****Whole breast irradiation**

7.211 Breast: 25 Gy (RBE) in 5 fractions of 5 Gy (RBE)

7.3 Treatment Technique

7.31 Radiation will be delivered using available scanning beam proton equipment at the treating institution or conventional radiation photon (x-ray) radiation.

7.4 Localization, Simulation, Immobilization

- 7.41 Simulation should be performed with the patient in the supine or prone position
- 7.42 Patients should be optimally positioned with a custom immobilization device at the discretion of the treating physician.
- 7.43 Arm position may be up or down.
- 7.44 The CT should extend cephalad to at least the level of the mandible to include both elbows and extend caudally to encompass the entire lung volume. The CT scan thickness will be 2mm.

- 7.45 External skin markers, which may include permanent tattoos, are recommended for daily set-up.
- 7.46 KV image guidance will be performed daily. Other imaging modalities, such as CBCT and Vision RT, real time tracking or others should be performed based on institutional guidelines and/or physician preference.
- 7.47 Volumetric imaging may be performed with re-planning at the physician's discretion.
- 7.48 **CT simulation** would be done with **contrast** to better define the tumor volume.

7.5 **Treatment Planning**

7.51 **Radiation Proton Planning**

- 7.511 For proton planning, 2 or more en face or oblique fields are recommended.

7.52 **Radiation Photon (x-ray) Planning**

- 7.521 Planning would be done based on tangent fields.
- 7.522 An inverse planned optimization is used to determine the beam weights to meet the target and critical structure dose-volume constraints and will be used for all left sided breast cancer patients pending insurance approval.
- 7.523 If IMRT is combined with the standard open medial and lateral tangential fields for whole breast irradiation, the IMRT beam as defined in Section 7.522 (1) should deliver > 50% of the total number of monitor units for the beam orientation.
- 7.524 3D field inside of a field would be used if IMRT is not approved by the insurance carriers.
- 7.53 Additional supraclavicular/axillary radiation
 - 7.531 In cases where more than two SLN are found to have disease or extra capsular extension is found additional radiation to the SCF/axilla area can be given at the discretion of the treating radiation oncologist. Doses fields and techniques would be defined by the treating physician. A matching anterior oblique field with an IMRT gradient based on prior dose distribution is encouraged.
- 7.54 Image guidance
 - 7.541 Cone beam CT would be done daily pre-treatment. Alternatively, if is not available CT on rails can be used. KV guidance can be used for proton therapy if volumetric guidance is not available. KV guidance can be used if conebeam is not an option

7.6 **Target Volumes**

The definitions for the CTV and normal structures for this protocol will generally follow the RTOG (Radiation Therapy Oncologic Group)-endorsed consensus guidelines for delineation for breast cancer [REDACTED] with exceptions described below.

7.61 Breast target volumes

- 7.611 **High tangents volume:** Alternatively, breast target volume can be defined by traditionally treated volume. All palpable breast tissue and all tissue encompassed by a standard tangent fields would be considered breast tissue. A medial tangent would be placed at the costo-condral

junction and a lateral tangent would be placed at the mid axillary line or more posterior as necessary to cover all breast tissue laterally. The caudal border would be 1 cm below all breast tissue. The superior border would be placed at the second intercostal space. Position would be verified on CT and in general it should not be closer than 1.5 cm from the inferior border of the humeral head and no more than 2 cm distally.

7.612 **Manual modifications:** alternatively, volumes can be defined using the RTOG breast atlas as above. However, for uniformity of the posterior margin the breast volume would include muscle tissue as needed to maintain a uniform distal edge. Please see breast CTV (section 7.6.1.3.2).

7.613 **Tumor:** Contour around the radiologic marker(s) including architectural distortion.

7.6.1.3.1 **Tumor CTV:** Tumor + 5mm 3 D expansion. Limit the CTV 5 mm from skin and not extending into the pectoralis muscle or chest wall.

7.6.1.3.2 **Breast CTV:** the breast would be the same as the CTV high tangents or low tangents without further expansions. The Tumor CTV is also included. The breast CTV volume is limited 5mm from the skin. The breast CTV posteriorly, would be limited by the chest wall.

7.7

Critical Structures

7.71 **Breast skin evaluation:** Will be defined as the first 3 mm of tissue under the body surface anterior to the Breast CTV.

7.72 **Heart:** To be contoured on all cases. The contour should begin just inferior to the level in which the pulmonary trunk branches into the left and right pulmonary arteries (PA) and should extend to its most inferior extent near the diaphragm. The esophagus, ascending and descending aorta and inferior vena cava should be excluded from the heart contour.

7.73 **Left anterior descending (LAD) interventricular branch (optional):** To be contoured on left-sided cases. “Originates from the left coronary artery and runs in the interventricular groove between the right and left ventricles. If it is difficult to see, raising the level and lowering the window may help (e.g. level 50, window 150)”.³⁵

7.74 **Right coronary artery (RCA) (optional):** To be contoured on all right-sided cases. “Originates from the right side of the ascending aorta. Due to the native heart position in the chest, on axilla CT, it appears to start inferior to the left coronary artery. It moves significantly with cardiac motion, so often the location can seem noncontiguous from axial CT slice to slice, as the position of the AV groove changes.”³⁵

7.75 **Ipsilateral lung:** To be contoured on all cases, auto-segmentation with manual verification is permitted

7.76 **Contralateral lung:** To be contoured on all cases, auto-segmentation with manual verification is permitted

7.77 **Total lung:** To be contoured on all cases, auto-segmentation with manual verification is permitted

7.78 **Contralateral breast:** Dose to the contralateral breast will not be constrained in treatment planning and therefore contouring of the contralateral breast is not required in this protocol. However, efforts should be made to limit inadvertent dosing of the contralateral breast.

